7.2 ENROLLMENT/BASELINE

Details for the opt-out process can be found in the attached *Opt out process* document. The initial patient opt out process is planned to last up to 4 weeks, with patients being given 1 week to opt out after receiving the Patient Information Sheet (PIS). All clinics will have the 12-week baseline data collected retrospectively. The estimated timeline for the staggered rollout of the study for the 20 clinics will begin with the first clinic opt out process in January 2023, and the last clinic post intervention data collection period ending in October 2024. We do not anticipate monitoring for changes in facility or participant eligibility during the course of the study.

The Patient Information Sheet (PIS) will be distributed to all patients during a hemodialysis session by an FMCNA study facility staff member. The Staff member will use wording similar to this script when giving the information sheet to the patients.

"This sheet tells you about a study from the University of Michigan that Fresenius Medical Care and our Medical Director have approved for our clinic. The goal of the study is to help patients feel better by taking steps to prevent low blood pressures during dialysis. All patients in the clinic will be in the study. However, after you review the details on this sheet you can choose to opt out of the use of your data by letting me know or by calling the toll-free number on the last page. You can also get more information about the study by calling the toll-free number."

The Dialysafe PIS will inform the patient about the Dialysafe Study data collection, provider intervention, follow-up period, and that the patient may be called about optional peer mentoring if the clinic is randomized to receive peer mentoring. The PIS will indicate that opting out means that the patient's data will not be shared, the Chairside questions will not be asked of him/her, and the patient will not be called to be offered peer mentoring. However, all patients in the 10 clinics randomized to the Provider Intervention will still receive the Provider Intervention because it is a facility-level intervention that will be applied to all ESRD patients. Refer to Table 4 for how opting out applies to the four types of study groups. If a patient opts out after data collection has started, the patient will be removed from data transfers from the date of opt out forward; 5 working days are allowed to process the opt out and discontinue the Chairside study questions.

Table 4 - Effect of Opting Out of Dialysafe According to Study Group

Study Group	# of Clinics	Effect of Opting Out ¹
Control Group	5	
• No data collection about that patient• No Chairside study questions asked of that patient
Provider Intervention Only (staff education and IDH checklist)	5	
• No data collection about that patient• No Chairside study questions asked of that patient• Provider Intervention still applies, regardless of opt out
Peer Mentoring Only	5	
• No data collection about that patient• No Chairside study questions asked of that patient• Patient will not be called and offered Peer Mentoring

Peer Mentoring + Provider Education (staff education and IDH checklist)	5	
 • No data collection about that patient • No Chairside study questions asked of that patient • Patient will not be called and offered Peer Mentoring • Provider Intervention still applies, regardless of opt out
--	---	--

¹If a patient opts out after data collection has started, the patient will be removed from data transfers from the date of opt out forward; 5 working days are allowed to process the opt out and discontinue the Chairside study questions.

After the initial opt out process, new patients (new to dialysis and new to the clinic) who enter the clinic will be offered opt out whose date of entering the clinic is ≥ 8 weeks prior to the end of the intervention period. However, to minimize staff time used to distribute the PIS, the PIS distribution will occur every 2 months to capture new patients who have been in the clinic for ≥ 30 days.

Patient participation in the study will be recorded in the form of an “ancillary order” in the patient’s electronic health record at FMCNA (called “eCC”). The Dialysafe Ancillary Order in eCC will be entered on all Dialysafe study patients who are eligible and do not opt out. The data entered in this Order will be retrieved by the FMCNA Custom Reporting and Data Analytics group team to identify study patient start and stop dates for the purpose of study data extraction. The Order will trigger two new Chairside questions programmed for the study to appear weekly as specified in the Order between the start and stop dates. The date on which the patient was given the patient information sheet will also be recorded in the Ancillary Order.

For recruitment into the Dialysafe Peer Mentoring Program, FMCNA staff will provide a card to patients in their clinic advising if they have been randomly selected to be offered peer mentoring, and letting them know to expect a call from UM staff to offer them peer mentoring. The card encourages them to pick up the phone when UM staff call (see “Peer Mentor Reminder Cards”). In the event that clinic staff identifies a patient as interested in learning about the peer mentoring program, but without regular access to a personal phone, UMSI study staff will mail a pre-paid phone to that patient. The phone may be used to reach UMSI study staff and NKF for the purpose of joining the peer mentoring program. UM staff will call patients up to 10 times to offer them peer mentoring, after which the patient will be listed as “could not be reached.” Each patient who cannot be reached or refuses will be replaced by the next randomly-selected patient (see “Recruitment and Retention Procedure Final”). Patient advocates within the clinics may discuss the peer mentoring program with patients who are willing to talk with them while waiting for treatment in the lobby or during a clinic-wide “lobby day” (if applicable).

University of Michigan Study Coordinator will use words similar to this script when calling patients to offer them peer mentoring.

“I’m calling to talk about a research study being done at your dialysis clinic. You should have received an information sheet about this study at your clinic. The study is being done by the University of Michigan, working with Fresenius Medical Care and the National Kidney Foundation. The goal of this study is to reduce the risk of low blood pressures during your treatments. As part of the study, we are now calling patients to offer a peer mentor program. I’d like to tell you more about this program- is that okay?” ... (If yes, continue...If no, thank the patient and end the call).

The goal of the peer mentoring program is to help patients feel better by coaching them on ways

to prevent low pressure during treatment. A peer mentor is someone who has been on dialysis and is trained and supervised by the National Kidney Foundation. If you choose to be in the program, you will be scheduled for five sessions with a peer mentor. The sessions will take place over 5-12 weeks. These will be done by using a computer tablet, which is like an iPad, that will be shipped to your house. You will be taught how to use the tablet so that you can watch a learning module before each peer mentor session. A learning module is like a set of slides with information viewed on the tablet's screen, and includes videos that shows you information while a voice reads the screen. The content of the modules is designed to provide you with ways to help you prevent and manage low blood pressures during your treatments. Each module will last about 1 hour and after each module, you will be asked to set a goal for your health. After the second time you meet with your peer mentor, we will send you a blanket from the University of Michigan. Additionally, you will receive an increasing stipend for every module that you complete. You will receive \$10 for completing the first module, \$15 for completing the second, \$20 for completing the third, \$25 for completing the forth, and \$50 for completing the fifth module and Peer Mentee Satisfaction Survey. These incentives total \$120 for the completion of the entire program. It is possible that some of the topics discussed with your peer mentor or in the goal setting part of the educational modules could make you feel uncomfortable. It is your choice whether to answer any question or discuss any topic. You can skip questions or discussion topics if you wish. You will be connected with your peer mentor for a live video-chat to go over what you watched and how you are doing with your goals based on what days and times work for you and your matched Peer Mentor. The topics you will discuss will include getting enough dialysis, using less salt, fluid limits, feeling better during treatments, and getting more involved in your care. All of your learning modules and talking to your peer mentor will take place in the comfort of your own home. The program and use of the tablet will be provided for you at no cost. At the end of the program, we do ask that you ship the provided tablet back to the University of Michigan. We will provide the required shipping materials and postage by mail so that participating in this program involves no cost to you. You need to know that if you join the peer mentor program, information about you and your peer mentor sessions will be entered into a database by the University of Michigan study staff and will be shared with your peer mentor and the National Kidney Foundation. This information will include your first and last name, gender, clinic name and ID, treatment day and shift, phone numbers, the dates when you start and stop the program, and how many sessions you completed. It may also include other information you share with your peer mentor such as the goals and personal values you identify as part of the program. The peer mentor sessions will not be recorded. After the program is over, the data will be sent to the University of Michigan Kidney Epidemiology & Cost Center to be analyzed, but only a code number will be used to identify your data. Your name and identity will be kept confidential. At the end of the peer mentoring program, you will also be asked to complete a survey that will ask your experiences and opinions about the peer mentoring program. As previously mentioned, by completing this survey, you will receive the full stipend amount of \$120 for finishing the entire program.

Joining the peer mentor program is voluntary and you can withdraw at any time. If you withdraw, your data will be used for the study only up to the time you withdraw. Do you have any questions I can answer? Would you like to sign up for the peer mentor program?"

Once a patient asks to be signed up for peer mentoring, their name and contact information will be shared with National Kidney Foundation who will match them with a mentor. They will also be offered the option of setting up a phone or web conference call with a UM study coordinator to learn how to use the Android tablet.

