Retention of participants in patient activation intervention. While participant retention is an issue in virtually any trial, dialysis patients are likely to experience fatigue, pain and other symptoms; thus there is a greater than average risk of patients not completing the intervention. In the two aforementioned published studies regarding peer mentoring and coaching for hemodialysis patients, participant retention rates were 85.7% for the 2-4 month study and 100% for the 10-week study, respectively.^{18, 153} Another study involving one-to-one peer support to people with diabetes had a 75.7% retention rate for a study that was 8-12 months long.¹⁵⁴ Notably, all of the aforementioned studies were more demanding than ours in terms of numbers of sessions with patients (8-30 sessions). Therefore, based on these prior studies, but recognizing the uncertainties of the COVID-19 pandemic, we estimate a retention rate of at least 73% for the peer mentoring intervention. In summary: if 60 patients in a facility are offered peer mentoring, we predict that approximately 30 of them will agree to receive peer mentoring; of these patients, at least 22 will complete the entire intervention. Under this circumstance, an additional 8 will thus complete part of the intervention.

In order to achieve our estimated retention rate of 65-75% for the complete intervention, and in keeping with published research,¹⁵⁵ our study team will use a combination of retention strategies. The following general evidence-based retention strategies will be used in

combination: patient/community involvement;¹⁵⁶ offering participant incentives;¹⁵⁶ using a participant-tracking database¹⁵⁷; using systematic methods for participant contact and scheduling of peer mentoring appointments;¹⁵⁶ issuing reminders prior to appointments;¹⁵⁶ interpersonal skill training for project staff;¹⁵⁷ monitoring retention;¹⁵⁶ and monitoring satisfaction with the study¹⁵⁸ via the planned peer mentoring survey.

Furthermore, we will follow best practices for retaining older and seriously ill study participants including: demonstrating care for participants by sending birthday or holiday cards;¹⁵⁸ flexibility in scheduling and dividing up peer mentoring sessions over time¹⁵⁸; facilitating home-based participation in the study;¹⁵⁸ developing a protocol for managing missed follow-ups;¹⁵⁸ and keeping response burden for patient data collection very low.¹⁵⁹

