5.4.4 Handling of Withdrawals

If facilities do drop out during the intervention phase, they will be replaced and the intervention will take place at a new facility. A facility would need to be replaced if: 1) they request to leave the study; or 2) 75% of the staff do not complete at least 90 minutes of training within the first 14-16 weeks of the intervention period. Data will be retained for facilities that withdraw from the study, unless they explicitly request that the data not be used. It is important to note that patients who drop out of the patient activation intervention will not be dropped from the overall study unless requested, and collection of outcome measures will continue. Data will be retained for patients who opt out of the study after the initial opt out period up until the decision to opt

out, unless otherwise requested by the patient. Any attrition (lack of participation in the patient activation intervention) could contribute to a reduced estimate of treatment effect in analyses using the intent-to-treat principle; this reduction in estimated treatment effect would appropriately reflect the expected effect of this intervention in the general dialysis population.

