With IRB waiver of consent and waiver HIPAA authorization with an opt out process, we expect that we will not have significant attrition due to patient withdrawal since interventions will be provided at the facility-wide level. Attrition may be seen in the patient activation (peer mentoring) intervention if patients choose not to participate in the peer mentoring program or if patients drop-out after starting the program. It is important to note that patients who drop out of the patient activation intervention will not be dropped from the overall study unless requested, and collection of outcome measures will continue. Any attrition (lack of participation in the

patient activation intervention) could contribute to a reduced estimate of treatment effect in analyses using the intent-to-treat principle; this reduction in estimated treatment effect would appropriately reflect the expected effect of this intervention in the general dialysis population.

A final type of attrition may be the possibility of missing data due to patients not completing the self-reported quality of life (KDQOL) survey or the patient symptom question regarding recovery time. For example, some participants may refuse to answer certain questions or may miss follow-up surveys. Where possible, we will note reasons for missing data by triangulating data sources to determine whether a patient has moved to another facility, or in accordance with two of our outcomes, been hospitalized or died (MD-4). Although every effort will be made to collect these data, some missing surveys are still likely, particularly among those in ill health. We do not expect missing surveys to be associated with study arm, but missingness itself can be analyzed for treatment differences as a tertiary outcome measure. The sample in each cross-section will include living patients only, so death will not be a problem as it would be in a longitudinal QOL study. We believe that this approach, along with our conservative assumptions regarding sessions needed as described previously, will largely prevent missing data for our primary outcome, as well as two secondary ones. Death will be tracked as an outcome, although the trial is not powered to assess this as a primary outcome. Data on subjects who leave the study site, will be used until their time departure from the study.

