14.3 INFORMED CONSENT PROCESS

I. Requested alterations to the informed consent process

PATIENTS

The patient information sheet contains content on the key elements of informed consent, but they will not be accompanied by a verbal dialogue to ensure informed consent nor records of having obtained consent. Staff at hemodialysis facilities will not obtain informed consent from patients.

For the overall study, at each participating facility, the following actions will take place:

- 1) A staff member (likely a patient care technician or nurse) will give each patient in the facility the patient information sheet, using the enclosed script.
- 2) On a list, the facility staff member or UM Study Coordinator will record the fact that each individual patient received the information sheet, and record any opt-outs from patients.
- 3) Patients may also call the UM School of Information research team via a 1-800 number ([name]) to ask questions and/or opt out of the study and/or discontinue peer mentoring.
- 4) The list of informed patients, including opt-outs, will be shared with an FMCNA nurse, who will create an "ancillary order" in the electronic health record for each patient who does not opt out of the study.
- 5) A list of patients participating in the study will be produced (and regularly updated); this will be kept in a research binder at each study facility.

To offer patients peer mentoring:

- 1) The patient information sheet indicates that patients may be contacted to offer them peer mentoring.
- 2) Using SharePoint, a secure computing environment hosted by FMCNA, the list of patients in the study, their sex, clinic, phone number and treatment schedule (to find the best time to call the patient) will be shared with the UM School of Information Study Coordinator.
- 3) The UM Study Coordinator will call the patient to offer them peer mentoring, using the script provided.

Patients without regular access to a personal phone will be sent a pre-paid cell phone if they indicate interest in the peer mentoring program to their clinic manager.

- 4) A volunteer Patient Advocate, as described in Section 5.3, may discuss the peer mentoring program with other patients or hand out a flyer ("Peer Mentor Program Flyer"). Discussion will be limited to that which is described in the "Patient Discussions" document; namely, the Patient Advocate's experience as part of the peer mentor program and the contact information for the UMSI study staff.

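### The mentoring call script can be heard as saying that leaving mentoring ends study use of a patient's data, whereas the protocol keeps collecting outcomes unless the patient asks otherwise

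*Combined protocol and SAP*

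**What the plan says.** - **Section 7.2, coordinator's script for offering mentoring.** "Joining the peer mentor program is voluntary and you can withdraw at any time". The next sentence is: "If you withdraw, your data will be used for the study only up to the time you withdraw".
- **Section 5.4.4, Handling of Withdrawals.** "patients who drop out of the patient activation intervention will not be dropped from the overall study unless requested"; outcome measurement goes on for them.
- **Section 11.4, Missing Data Issues.** The same rule appears in the analysis plan: such patients "will not be dropped from the overall study unless requested, and collection of outcome measures will continue". It supports the argument that poor uptake dilutes the intent-to-treat estimate in a way that reflects real use.
- **Section 7.2, opt-out text and Table 4.** Stopping the data is tied to opting out of the study: "the patient will be removed from data transfers from the date of opt out forward". Extraction follows start and stop dates in the Ancillary Order, which is entered for eligible patients who have not opted out.
- **Section 14.3.** The toll-free line lets a patient "opt out of the study and/or discontinue peer mentoring", so these are listed as two acts.

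**The concern.** The script attaches to leaving mentoring the consequence that sections 5.4.4 and 7.2 attach to opting out of the study. A patient who withdraws after hearing it may believe that use of their dialysis records has ended, while the protocol goes on using them.

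Two things are at stake. The first is the accuracy of what patients are told. The trial seeks a waiver of consent and relies on an information sheet and opt-out, so statements about when data use stops are a central part of the protection offered. The second is the comparison itself. The script is used only where mentoring is offered. If staff act on it, follow-up is shortened after randomisation in the patient-activation clinics and, by this route, nowhere else. That conflicts with the intent-to-treat plan.

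**Working it through.** **1. Which rule governs?**

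| Event | Script (7.2) | 5.4.4 and 11.4 | Data flow (7.2, 14.3) |
|---|---|---|---|
| Leaves mentoring only | Study use of data ends at withdrawal | Stays in study; outcomes still collected unless the patient asks otherwise | No change to the Order or the transfers is described |
| Opts out of study | Not addressed | Data kept up to the opt-out | Transfers stop from the opt-out date |

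The conflict is in the first row. The exception for a patient's request does not remove it. Under 5.4.4 a request is something beyond dropping out, whereas the script says withdrawal alone is enough. Nothing tells staff whether a withdrawal made on the strength of the script counts as such a request. The mentoring report (section 14.5, Table 10) carries a stop date but no field for whether the patient withdrew or what they asked about their data.

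Only study opt-out is linked to stopping transfers, so the likelier outcome is that the data continue to flow.

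**2. How many patients could be affected?**

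Inputs: 30 mentees in each of 10 clinics (section 5); 22 expected to finish and "an additional 8 will thus complete part of the intervention" (section 5.3); 600 patients in the patient-activation clinics (Table 1).

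- The plan's retention figure reproduces: 22/30 = 73%.
- Partial completers: 8 × 10 = 80, and 80/600 = 13.3%.
- Over the 65–75% retention range also given in 5.3: 300 × 0.25 = 75 (12.5%) to 300 × 0.35 = 105 (17.5%).

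These are partial completers, not formal withdrawals. No formal-withdrawal rate is given. Section 7.3 describes patients who miss sessions and stop responding, and has staff contact them to ask whether they wish to continue; that could turn some silent dropouts into explicit ones. The range is therefore 0 to about 80 at the plan's 73%.

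**3. What would honouring the script do to the primary analysis?**

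It would truncate a patient's data, not delete them. The main model uses patients with at least 60 sessions (section 11.4). At three sessions a week (section 2.1.3), 60/3 = 20 weeks, and the 24-week intervention period yields 24 × 3 = 72 sessions. Counted from the start of the intervention, a patient cut off before week 20 leaves the main model. If the 12 baseline weeks also counted (12 × 3 = 36 sessions), the threshold would be reached after (60 − 36)/3 = 8 intervention weeks. The plan does not state the counting period. The logistic sensitivity analysis keeps all patients.

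**4. Power.**

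With k = 10 facilities per group, m₁ and m₂ patients per facility and ICC ρ = 0.10:

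SE = SD × √[(1 + (m₁ − 1)ρ)/(k·m₁) + (1 + (m₂ − 1)ρ)/(k·m₂)]; power = Φ(D/SE − 1.96).

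For D = 0.034, SD = 0.08 and m₁ = m₂ = 60: SE = 0.08 × √(2 × 6.9/600) = 0.01213, so power = Φ(2.80 − 1.96) = 0.800.

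| D / SD | Table 5 | Reproduced | 52 per mentoring clinic |
|---|---|---|---|
| 0.034 / 0.08 | 80% | 0.800 | 0.796 |
| 0.034 / 0.10 | 61% | 0.611 | 0.607 |
| 0.040 / 0.08 | 91% | 0.909 | 0.907 |
| 0.043 / 0.10 | 81% | 0.809 | 0.805 |

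Even complete loss of 8 patients per mentoring clinic costs at most 0.4 points.

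**5. Bias.**

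If patients were lost outright, bias = share lost × difference in IDH rate between those lost and those kept. The documents give no such difference.

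**The case against.** The best defence is that the sentence concerns mentoring data only. Just before it, the script lists what joining the program generates, says those data go to the analysis center under a code, and never mentions routine dialysis records. On that reading it agrees with 5.4.4 and 11.4. Patients have also already received an information sheet explaining that opting out of the study stops data sharing, and coordinators use words similar to the script, not necessarily its exact text. The information sheet and the recruitment and retention procedure are attachments not available here.

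The narrower reading is possible, so this is not a flat contradiction on every reading. It does not settle the matter. The script opens by describing a research study and offers mentoring as one part of it; the withdrawal sentence then speaks of use for the study, with no limit to program records. A patient can fairly hear it as covering everything, and the earlier sheet does not tell them otherwise at the moment they decide.

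The defence is also right that no section makes mentoring withdrawal stop data transfers. Arm-specific data loss is therefore the less likely branch.

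**Conclusion.** The concern holds as an inconsistency between what mentees are told and what the protocol does. The rule in 5.4.4 and 11.4 is clear, stated twice and suited to intent-to-treat; the script sentence is what needs to change. The likelier consequence is continued use of outcome data after some patients were told it would stop. The alternative is truncation confined to the 10 patient-activation clinics, with possible exclusion under the 60-session rule depending on how sessions are counted.

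The number affected is unknown, from 0 to about 80 of 600 (13%), and the power effect is under 1 point.

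A reader might infer that the mentoring arms will lose 13% of their patients and that the mentoring effect will be overstated substantially. For example, an assumed 5–10 point higher IDH rate in dropouts gives 0.133 × 5 = 0.7 to 0.133 × 10 = 1.3 points, or 16% of the 4.3-point target (0.67/4.3) to 39% of the 3.4-point target (1.33/3.4). The documents do not support that as an estimate. It assumes that every partial completer formally withdraws, that their data are removed entirely rather than cut at withdrawal, that staff follow the script over the written data flow, and a rate difference found nowhere in the plan. It is at most an illustrative upper bound.

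**What to change.** - Reword the script sentence so that leaving mentoring ends mentoring only, and routine dialysis records continue to be used unless the patient also opts out of the study. Say how to do that.
- Record leaving mentoring and opting out of the study as two separate fields, and stop data transfers only for the second.
- For patients recruited under the present script, obtain an IRB ruling on how their data are handled, and report the number affected by arm.

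The cost is an IRB amendment to one sentence, one added tracking field and a count of those already recruited. The downside is that a few patients, told plainly that their records will still be used, may choose a full opt-out.
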